4. STUDY ASSESSMENTS AND PROCEDURES

4.1. Patient Screening and Assessment

The patient informed consent form is outlined in Appendix 2 and the survey instrument for the patient assessment is in Appendix 3. The questionnaire will begin with a screening module with questions to confirm eligibility. Depending on the answers to the screening questions, survey participation could either be terminated or continued. If ineligible, the respondent is immediately notified with a “thank you” message that survey participation has ended. If eligible, the respondent is allowed to continue survey participation.

After accepting the invitation to participate in the study, individual patients will be directed to take a screening questionnaire based on their preference of either online completion or via a telephone interview. The screening questionnaire will assess:

- Agreement to take the survey
- TROBALT formulation, time since last prescription.
- Demographics: age. Additional socio-demographic questions will be asked in the main survey questionnaire.
- Employment at GSK or [REDACTED]

4.2. Neurologist Screening and Assessment

The health care provider introduction information is outlined in Appendix 4, and the survey instrument for neurologist assessment is in Appendix 5. The neurologist questionnaire will begin with a screening module with questions to confirm eligibility. Depending on the answers to the screening questions, survey participation could either be terminated or continued. If ineligible, the respondent is immediately notified with a “thank you” message that survey participation has ended. If eligible, the respondent is allowed to continue survey participation.

The screening questions included in the prescriber survey are:

- Agreement to take the survey
- Time since the last prescription written for any AED
- Ever prescribe TROBALT*
*Used to ensure that the sample includes at least 100 TROBALT prescribers
- Employment at GSK or [REDACTED]

4.3. Patient Outcomes

Patient understanding of the significant risks associated with TROBALT will be assessed using a standardised questionnaire.

The primary outcome of this study is the proportion of patients that correctly respond to individual survey questions concerning the risks associated with TROBALT. The proportion responding correctly will be tabulated separately for each item in the patient understanding survey instrument. These risks represent those described in the PIL for TROBALT.

Patient demographic information will be collected at the end of the survey in order to further characterize the respondent population. This will include gender, country of residence, education level and indication for TROBALT use.

At the conclusion of the online survey, the final screen will display a summary of the relevant information from the PIL, including a link to the PIL on the internet at <http://www.gsk.com/products/prescription-medicines/trobalt.htm>. Similar information will be provided by the telephone interviewer. If the patient poses any questions on the information presented, he/she will be directed to discuss the question with the treating physician.

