3. INVESTIGATION PLAN

3.1. Study Design

This study is sponsored by GlaxoSmithKline (GSK), and will be conducted by [REDACTED] an international research consultancy.

This is a cross-sectional study of physicians' and patients' understanding of the significant risks associated with TROBALT.

Physicians will be recruited by selecting a random sample of neurologists from lists provided by GSK in each country. The list includes names of all potential TROBALT prescribers who were mailed an introductory letter including the Physician's Guide for TROBALT (Appendix 1). Following recruitment, neurologists' understanding of the potential risks associated with TROBALT will be evaluated using an online survey. Each invitation will include information on how to access the survey on-line, and will include a unique code to ensure that the invitation is used only once.

The primary method of recruiting patients is through their physicians. In countries in which a list of current TROBALT prescribers can be obtained, a random sample of prescribers in each country will be selected. Otherwise, the sample will come from the list of neurologists who were mailed the Physician's Guide, who have not participated in the neurologist survey. Sampled prescribers will be asked to provide survey invitations to their patients being treated with TROBALT. Each prescriber will be given 10 invitations and asked to provide these invitations to up to 10 consecutive patients who have been prescribed TROBALT in the last 3 months. If the patient response rate using this recruitment method is lower than expected, then other options will be identified including patient panels where available.

Following recruitment, patients' understanding of the potential risks associated with TROBALT will be evaluated using an online survey or the same survey instrument delivered during a telephone interview. The latter option aims to accommodate individuals who are not comfortable with online technology or are not computer literate. Each invitation will include information on how to access the online survey and will also provide the toll-free number for accessing the Survey Call Centre.

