3.3.1. Questionnaire Structure

Each survey will be composed of multiple choice and close-ended questions. There will be no open-ended questions included. For statements or questions that use "true" or "yes" vs. "false" or "no" response options, the desired response for key risk messages is generally "true" or "yes" indicating knowledge of, or behavior in accordance with, the objectives of the program. However, some questions are formatted to have the respondent disagree with the statement as written by providing response options of "false" or "no" to avoid having the same affirmative answer for all desired responses.

Both physicians and patients will be provided a unique code in the survey invitation letter and will be asked to provide the unique code to gain access to the online survey or when calling the Survey Coordinating Center. The code will be deactivated after use to minimize the possibility for fraud.

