4.4. Neurologist Outcomes

Neurologist understanding of the significant risks associated with TROBALT will be assessed using a standardised questionnaire.

The primary outcome of this study is the proportion of neurologists that correctly respond to individual survey questions concerning the risks associated with TROBALT. The proportion responding correctly will be tabulated separately for each item in the physician understanding survey instrument. These risks represent those described in the Physician's Guide for TROBALT.

Physician demographic information will be collected at the end of the survey in order to further characterise the respondent population. This will include gender and medical specialty, type of medical practice, years in medical practice. Country in which practice occurs will be collected at the beginning of the survey in order to identify respondents from Switzerland for whom not all questions apply.

At the conclusion of the online survey, the final screen will display a summary of the relevant information from the Physician's Guide.

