9.4. Study reporting and publications

The recruitment period is estimated to be 12 months from November 2012, though this could be earlier if the target number of participants is reached sooner than November 2013.

A final report will be written and submitted to European Medicines Agency (EMA) through the Periodic Safety Update Report (PSUR) in May 2014 (PSUR scheduled 29th September 2013 to 28th March 2014).

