Neurologist told me			
Family doctor or general practitioner (GP) told me			
Online			
Patient Information Leaflet			
Patient Support Group			

16. The Patient Information Leaflet says TROBALT can cause heart problems. Which one of the following heart conditions can TROBALT cause? (Select one answer)

- Chest pain
- **Making my heart beat too fast or too slow**
- Heart attack
- All of the above
- None of the above

17. Which of the following raises the chance for effects on heart rhythm when you take TROBALT? Please answer “yes,” “no” or “I don’t know” for each one.

	Yes	No	I Don’t Know
Taking other medicines	X	O	O
Smoking	O	X	O
Already having a heart problem	X	O	O
Having asthma	O	X	O
Being 65 years old or older	X	O	O

18. In what country do you live? (Will have drop-down menu of all countries in the survey).

19. What is your gender?

- Male
- Female

20. What is the highest level of education you have completed?

- Some secondary school (EU equivalent) or less
- Finished secondary school
- Some university or technical/trade school
- Graduated university
- Post graduate studies
- Prefer not to answer

[CLOSING] Thank you for completing the survey. The following are the correct answers to the survey questions about TROBALT.

The following are the correct answers to the survey questions about TROBALT.

Which side effects are more likely to happen with TROBALT?

- Cannot pass urine (urinary retention)
- Being confused
- Seeing or hearing things that are not there (hallucinations)
- Severe mental problems, such as being out of touch with reality (psychotic disorders)

You should call your doctor right away if you have which symptoms?

- Trouble starting to pass urine (urinary retention)
- Thoughts of harming or killing yourself (suicidality)

The Patient Information Leaflet says TROBALT can cause heart problems. Which heart condition can TROBALT cause?

- Making my heart beat too fast or too slow

Which factors raise the chance for effects on heart rhythm when you take TROBALT?

- Taking other medicines
- Already having a heart problem
- Being 65 years old or older

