19. Using the Treatment Initiation Pack, by which week can the patient reach a dose of 600mg/day?
- 2 weeks
 - **3 weeks**
 - 4 weeks
 - 5 weeks
 - None of the above
20. At what dose has TROBALT been shown to produce a possible QT prolonging effect?
- 600 mg
 - 900 mg
 - **1200mg**
 - 1800 mg
 - I don't know
21. For which patients is it recommended that an ECG is recorded before initiating TROBALT? (Please select all that apply.)
- Patients with hypertension
 - **Patients with congestive heart failure**
 - **Patients with ventricular hypertrophy**

- **Patients with hypokalemia**
 - All of the above
 - None of the above
 - I don't know
22. What should you do in a patient with a QTc of **more** than 440ms before starting TROBALT? (Please select the best response)
- Recheck the ECG 1 week after the first dose
 - Recheck the ECG at monthly intervals
 - **Recheck the ECG after reaching the maintenance dose**
 - I don't know
23. Which new cardiac effects in particular should you warn your patients about after prescribing TROBALT? (Please select all that apply)
- Syncope
 - Palpitations
 - Any other symptoms of arrhythmia
 - **All of above**
 - None of the above
24. How would you classify your primary medical specialty?
- Neurology
 - Neurosurgery
 - Epileptology
 - Other (specify) _____ [FREE TEXT]
 -
25. Have you read the TROBALT information letter that was sent at the launch of TROBALT?
- Yes
 - No
 - I don't know
26. From which of the following sources have you learned about the risks associated with use of TROBALT? (Please select all that apply)
- TROBALT launch letter
 - GlaxoSmithKline medical information
 - Other health care professionals
 - GlaxoSmithKline promotional materials
 - GlaxoSmithKline sales representatives
 - Journal article
 - GlaxoSmithKline-sponsored educational meeting
 - None of the above

27. What is your gender?

- Male
- Female

28. For how many years have you been in medical practice?

- Less than 3 years
- 3-5 years
- 6-10 years
- 11-15 years
- 16-20 years
- More than 20 years
- Prefer not to answer

29. Do you agree to provide your name and address so that we can issue a payment for your time in completing this survey?

- Yes (Record name and address)
- No

Name _____

Address _____

[CLOSING] That ends the survey. Thank you again for your help. The correct answers to the questions about TROBALT follow.

The following are the correct answers to the survey questions about TROBALT.

For which condition is TROBALT approved for use?

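### The closing scripts show an item-by-item answer key instead of the promised summary while recruitment is still open; any leakage could only push the primary proportions up, probably by little

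*Protocol*

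**What the plan says.** **Promised closing screen.** Section 4.3 says that for patients "the final screen will display a summary of the relevant information from the PIL", with a link to the leaflet. Section 4.4 says that for neurologists "the final screen will display a summary of the relevant information from the Physician's Guide".

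**Scripted closing screen.** The patient script in Appendix 3 opens with "Thank you for completing the survey. The following are the correct answers to the survey questions about TROBALT". It then restates Q13, Q14, Q16 and Q17, each with its keyed response, and ends with the leaflet's web address. The neurologist script in Appendix 5 announces "The correct answers to the questions about TROBALT follow" and goes through Q6 to Q23, omitting Q19 and Q20 for Swiss respondents. For two items (Q9 and Q11) it reprints wrong options and tags the right one.

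**Timing.** Section 9.4: "The recruitment period is estimated to be 12 months from November 2012", or less if targets are met sooner.

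**Access control.** Section 3.1 says each neurologist invitation "will include a unique code to ensure that the invitation is used only once". Section 3.3.1 gives patients and physicians a unique code and adds: "The code will be deactivated after use to minimize the possibility for fraud". Section 3.3.2 bars going back to an answered question. Section 8 keeps the prescribers who invite patients separate from those surveyed. Section 3.2.2.3 sends a reminder only where there was no response.

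**Screening.** Neither the topics listed in Sections 4.1 and 4.2 nor the screening questions in Appendices 3 and 5 ask about earlier participation or sight of the questions or answers.

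**The concern.** The restated items are the primary outcome: Sections 4.3 and 4.4 define it as the proportion answering each risk question correctly. Early completers therefore leave with the answers while later respondents are still being recruited. Respondents are not isolated from one another. Each inviting prescriber hands out up to 10 invitations to consecutive patients (Section 3.1), and neurologists within a country are drawn from one mailing list.

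The safeguards act on the invitation. They do not reach two routes:

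- answers passing from one respondent to another;
- one person completing twice with two codes, for example through a prescriber and later through a patient panel, which Sections 3.1 and 3.2.1.3 allow if response is low.

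At stake is a bias in one direction. Someone who has seen the key can be expected to do better, so the educational plan would look more effective than it is. A larger sample does not reduce this. Neither the bias measures in Section 3.3.2 nor the limitations in Section 8 mention it.

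**Working it through.** **1. The plan's own precision figure.** Section 7 gives ±6.0 points for 250 patients at 60% correct. The Wald half-width is 1.96 × √(0.60 × 0.40 / 250) = 6.07 points, so the figure reproduces apart from rounding.

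**2. Size of the bias.** Let c be the share of completions made after sight of the key, p the true proportion correct and k the proportion correct among those who saw it. Then

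bias = c × (k − p).

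Only the margins come from the protocol (Section 7, Table 1). The values of c and k are assumptions, and p is varied.

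| Assumed k | True p | c = 2% | c = 5% | c = 10% | Stated margin, n = 250 |
|---|---|---|---|---|---|
| 95% | 50% | +0.9 | +2.25 | +4.5 | ±6.0 |
| 95% | 60% | +0.7 | +1.75 | +3.5 | ±6.0 |
| 95% | 80% | +0.3 | +0.75 | +1.5 | ±4.8 |
| 100% | 60% | +0.8 | +2.0 | +4.0 | ±6.0 |

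For example, 0.05 × (95 − 60) = 1.75 points. The bias shrinks as p rises and vanishes for items nearly everyone already answers correctly.

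**3. Share needed to equal the margin (p = 60%).**

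- k = 95%, n = 250: 6.0 / 35 = 17%, about 43 patients.
- k = 100%, n = 250: 6.07 / 40 = 15%, about 38 patients.
- k = 95%, n = 200 (the neurologist target outside Germany): Table 1 gives ±7.0, so 7.0 / 35 = 20%, or 40 neurologists.

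**4. Effect on the interval.** A bias below the margin still costs coverage. With n = 250, p = 60% and k = 95%, take the standard error at the reported proportion and a normal approximation:

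- c = 2%: reported 60.7%, SE 3.09, shift 0.7 / 3.09 = 0.23 SE, coverage about 94%.
- c = 5%: reported 61.75%, SE 3.07, shift 1.75 / 3.07 = 0.57 SE, coverage about 91%.
- c = 10%: reported 63.5%, SE 3.05, shift 3.5 / 3.05 = 1.15 SE, coverage about 79%.

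At 2% the interval is hardly affected. At 10% it would be, but nothing in the protocol points to a share of that size.

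**The case against.** The strongest reply is that the key adds little. It restates PIL or Guide content, so calling it a summary is loose wording, and a true summary would reveal much of the same information. Patients may have the PIL beside them, as Section 8 admits, and neighbouring neurologists were mailed the Guide. Much of this stands. However, drawing on the PIL or Guide is part of what the survey sets out to evaluate, whereas drawing on the key is not, and the key shows exactly which items are scored and how.

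Repeat completion is also hard. It needs a second code. Invitations are meant for different consecutive patients, panels are only a contingency, and reminders go only to non-responders. This stands too: repeats are probably few, and sharing between respondents is the more credible route. Appendices 2 and 4 and the invitation letters are not in the text at hand, so a one-response instruction there cannot be ruled out.

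A reader might infer that code deactivation is the only control, or that contamination could never be found afterwards. The documents do not support either. The other safeguards are listed above, and the name and address taken for payment at Q29 could expose neurologists who were paid twice.

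Finally, correcting misunderstandings at once is a reasonable aim in a risk-communication survey. That is true, and an immediate summary would still serve most of it.

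**Conclusion.** The point holds as a modest design weakness. The body of the protocol promises a summary; the scripts deliver an itemised key to the primary-outcome questions during open recruitment; and no screener item covers earlier participation or sight of the answers. Any resulting bias could only run upward, provided that people who have seen the key do at least as well as they otherwise would.

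Its size cannot be determined from the documents. With 95% correct after seeing the key and a true 60%, it is 0.7 to 3.5 points for an affected share of 2% to 10%, below the stated ±6.0 points. About 17% of completions would have to be affected to match that margin. The effect is therefore probably small.

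A reader might conclude that the primary proportions will be inflated. The documents support only that they could be, because no affected share is stated or can be derived.

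**What to change.** 1. **Closing screen.** While the survey is open, replace the closing scripts in Appendices 3 and 5 with the summary that Sections 4.3 and 4.4 already promise: PIL or Guide content by topic, with the PIL link for patients, and without the question wording and keyed options. The telephone script should match.
2. **Screener.** Add one item to Appendices 3 and 5, and to the lists in Sections 4.1 and 4.2, asking whether the person has already taken this survey or seen its questions or answers. Exclude those who say yes from the primary tabulation and report their number.
3. **Limitations.** Add a sentence to Section 8 on possible answer sharing between respondents.

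Checking the Q29 payment details for duplicates is routine data management. It is worth doing, but the point does not depend on it.

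If the itemised key is kept for later release, two mismatches with the questionnaire must be reconciled first: the direction of the 440 ms threshold in neurologist Q22, and the urinary term in brackets in patient Q14.

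**Cost.** One script and one question, changed before programming. Item-level feedback is delayed, and for patients it may be lost, since they are reached through prescribers and no channel for later contact is described. The screener relies on self-report: it will lose some honest respondents and miss anyone determined to repeat.

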4.4. Neurologist Outcomes

Neurologist understanding of the significant risks associated with TROBALT will be assessed using a standardised questionnaire.

The primary outcome of this study is the proportion of neurologists that correctly respond to individual survey questions concerning the risks associated with TROBALT. The proportion responding correctly will be tabulated separately for each item in the physician understanding survey instrument. These risks represent those described in the Physician's Guide for TROBALT.

Physician demographic information will be collected at the end of the survey in order to further characterise the respondent population. This will include gender and medical specialty, type of medical practice, years in medical practice. Country in which practice occurs will be collected at the beginning of the survey in order to identify respondents from Switzerland for whom not all questions apply.

At the conclusion of the online survey, the final screen will display a summary of the relevant information from the Physician's Guide.

4.5. Adverse Drug Experience/Event Measures

This study will not investigate adverse events associated with the use of TROBALT. While it is not the intention of the survey to solicit adverse events, it is possible that during a telephone survey a respondent may spontaneously provide information that meets the criteria of an adverse event. Any reported adverse events will be entered into the GSK safety database:

- Online respondents will be provided with the telephone number for the local call centre in the country of the participant at the end of the online survey and will be directed to call the centre to report any adverse events potentially associated with TROBALT.
- If, at any time during the telephone interview, the subject describes an adverse event associated with TROBALT or any GSK product, the telephone interviewer will complete an adverse event form and fax it to GSK Global Clinical Safety and Pharmacovigilance on [contact] within 24 hours of receiving the information. The form is included in Appendix 6.
- GSK Global Clinical Safety and Pharmacovigilance has specific guidelines detailing action to be taken if an individual reports suicidal thoughts or behavior. All telephone interviewers will be trained on these guidelines and will follow this process if a respondent reports suicidal thoughts during the interview.

At the end of the project, [REDACTED] will provide a summary of all adverse events that it has submitted to GSK to enable the reports to be reconciled.

5. DATA COLLECTION AND MANAGEMENT

All data collected during the survey will be held confidential. The electronic data capture (EDC) system used for data collection encrypts all identifiable information, and respondent identifiers are stored separately from the survey responses.

In all cases, patient identifiers will not be collected or transmitted to GSK according to GSK policy. All patients will be given an alphanumeric patient identifier.

